Inter-pregnancy intervals of less than 24 months are associated with higher rates of newborn and child mortality, as well as higher probability of pre-term and low birth weight newborns, and malnutrition and stunting among children under five (Kozuki et al, 2013; Cleland 2012). An MCHIP secondary analysis of the 2011 Ethiopia DHS (MCHIP 2013) revealed that among all non-first births, 47% of pregnancies occur at less than the 24 month inter-pregnancy interval (13% of women are pregnant before the end of the first year postpartum). Looking at prospective unmet need (defined as whether women would like another child within the next two years), among Ethiopian women 0-2 years postpartum ($n = 4,453$), 94% of women did not wish another pregnancy at the time of the survey yet only 19% used a modern method of contraception, resulting in a prospective unmet need among postpartum women of 74%. This compares to an unmet need of 34% among postpartum women using the standard DHS method of calculating unmet need which uses a question about the desire for the recently born child for the subset of postpartum women in the total sample (Moore et al, 2015).

Exclusive or predominant breastfeeding offers protection against rapid fertility return during the first 6 months after childbirth; however, rates of exclusive and predominant breastfeeding drop off rapidly in Ethiopia starting in the second month of life. While 70% of newborns (0-1 month) are exclusively breastfed, only 32% of infants 4-5 months old are exclusively breastfed. Only 4% of children 6-23 months are fed appropriately based on infant and young child nutrition (IYCN) recommendations and 44% of children less than 5 years of age are stunted (DHS 2011).

Women in Ethiopia do not access formal health services as frequently as they should. Only 43% access any antenatal care services and 19% are seen for at least 4 ANC visits during pregnancy, with wide differences between urban and rural women. The majority of births (89.5%) still occur at home, are not attended (3.8%) or attended by a traditional birth attendant (TBA) (28.4%) or relative (56.6%). Only 6.7% of mothers and babies had a postnatal check within two days of birth. Vaccination coverage is higher with BCG at 79.6%, DPT-HepB-Hib1 at 80.0%, DPT-HepB-Hib3 at 65.7%, OPV1 at 90.1%, OPV3 at 70.5%, and measles at 68.2% (Ethiopia NICS 2012), though it falls short of international recommendations of country coverage of over 90%.

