This study will be implemented 2 primary health care units (PHCUs), comprised of one health center and all kebeles/health posts in their catchment area, in Hitosa Woreda and 2 PHCUs in Lude-Hitosa Woreda. We randomly assigned 1 PHCU in each Woreda to the intervention and control arms. So out of 4 PHCUs in each Woreda, 1 was selected for intervention and 1 for control.

We obtained the total population for each PHCU. To estimate the number of women age 15-49 and expected pregnancies at the time of study survey, we used results from the Ethiopia mini DHS 2014: 43.6% of female residents of selected households were age 15-49 and 7.3% of women age 15-49 were currently pregnant at the time of the Mini DHS 2014.

Table 3: Estimation of eligible population

Arm	Total population	Female population (50%)	Expected females age 15-49 (43.6% of female pop)	Expected current pregnancies (7.3% of women 15-49)	Women 6-9 months pregnant (pregnancies / 3)
Intervention	72,138	36,069	15,726	1148	382
Comparison	52,508	26,254	11,446	835	278

For pregnant women, we calculated the minimum sample size requirements for this quasi-experimental design for the main outcome of interests (adoption of LAM and other modern method by 12-month PP) using the formula:

$$n' = \frac{\{z_{1-\alpha/2}\sqrt{2\bar{p}(1-\bar{p})} + z_{1-\beta}\sqrt{p_1(1-p_1) + p_2(1-p_2)}\}^2 (1 + (m-1)\rho)}{(p_1 - p_2)^2}$$

where, $p = (p_1 + p_2) / 2$

Where p_1 and p_2 are the proportions of women adopting LAM or other modern method in the intervention and control arms, respectively, and Z's are the critical value of the normal distribution at $\alpha=0.05$ and $\beta=0.20$; $1+(m-1)\rho$ captures the design-effect due to cluster based sampling of areas, where m = average size of the clusters and ρ =intra-cluster correlation. We consider a design-effect (deff) of 1.5 for adjusting higher intra-cluster correlation in the observations in the quasi-experimental design.

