We require a minimum of 299 women in postpartum observation period in each arm to detect an increase of at least 10% contraceptive prevalence rate (CPR) in the intervention arm, compared to the women in the control arm (20% vs 10% in the intervention and control arm, respectively) with $deff=1.5$ at 80% statistical power. Assuming about 20% lost-to-follow-up and non-response rate, we target to enroll 375 women in each arm. We consider that it will be sufficient to select 1 PHCU and its attached *kebeles* in each of the two *woredas* to ensure adequate sample size, with 2 PHCU randomly assigned to the intervention area (1 per *woreda*) and 2 to the control area (1 per *woreda*). The eligible women in 3rd trimester who consent to participate in the study voluntarily will be recruited and be interviewed at enrollment and at 12-month PP.

We used $p_1=0.2$ (20% PP contraceptive uptake by the final round of observation in the intervention arm) and $p_2=0.1$ (10% in the comparison arm). We considered $deff=(1+[m-1]\rho)= 1.5$. Because we are targeting 375 sample size of pregnant women in each arm consisting of 2 PHCUs, this implies $m=188$ AND $\rho=0.0027$.

Because the selected PHCUs are adjoining *woredas* of the same zone, it is expected that they will be quite similar, and in addition, the underlying population are all similar in terms of postpartum status; hence ρ very small (the larger the heterogeneity, the larger the ρ value). The Ethiopia DHS 2011 results suggest that the $deff$ of contraceptive use in all 11 regions are much smaller than the national level $deff$ of CPR (Appendix B – Estimates of Sampling Errors); *woreda* level $deff$ is expected to be much smaller due to less heterogeneity at *woreda* level, compared to the region/state level. In all regions, method specific $deff$ was <1.5 . So, we considered that of $deff=1.5$ is applied in this study is reasonable and practical. A study on postpartum use of contraceptive method at a *woreda* level in Ethiopia also had $deff=1.5$ (Abera Y, Mengesha ZB, Tessema GA. Postpartum contraceptive use in Gondar town, Northwest Ethiopia: a community based cross-sectional study. BMC Women's Health. 2015;15:19.)

Sample size requirements are included below based on the average number of providers and HDAs and managers in each *kebele*. See Table 4: Sample Size Summary

Table 4: Sample Size Summary

Study Participant	Intervention (2 PHCU)	Comparison (2 PHCU)	Total
Pregnant women	375	375	750

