We will fit multivariable logistic regression models for the primary and secondary binary outcomes (see below) to examine differences between the study arms, adjusted for confounding covariates and clustering at kebele level. We will also conduct a “per-protocol analysis” by examining the “dose-effect” of health system contacts on the primary and secondary outcomes, regardless of study arm. We will run two dose-effect models, looking at the association between the outcomes and 1) the total number of contacts and 2) the number of contacts during which FP was discussed as reported by the woman. For the secondary outcome, we will only include contacts during pregnancy since contacts after the birth would not have a temporal effect on whether the woman chose a method prior to delivery.

- Primary outcome:
  - Proportion of interviewed postpartum women who used a modern family planning method within 12 months after giving birth
- Secondary outcome:
  - Proportion of interviewed postpartum women who chose a method prior to delivery

We will also conduct time-to-event analyses using life-table method and use a log-rank test to test for differences in survival distributions between the study arms in terms of the timing of FP uptake after birth. We will perform multivariable hazards model (Cox’s proportional model or parametric model with Weibull distribution in case of non-normality in hazards function) for adjusting confounding covariates and clustering effects.

Additionally, we will run hazards regression models for women who initiated exclusive breastfeeding/LAM after birth to test for differences between arms in the duration of exclusive breastfeeding/LAM use.

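### The primary outcome is ever-use of a modern method within 12 months, so women who start and stop count as successes; no primary, secondary or modelled outcome measures use at 12 months, and the sample-size section gives the same 20% vs 10% three different names.

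*SAP*

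**What the plan says.** SAP section A defines the primary outcome as "Proportion of interviewed postpartum women who used a modern family planning method within 12 months after giving birth". It requires no continued use and gives no rule for women who stop or conceive again. It does not say whether LAM is a modern method.

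The single secondary outcome is choosing a method before delivery. The survival analysis is of time to uptake, and the only duration models are for exclusive breastfeeding/LAM. Reasons for starting and stopping, and duration of use, are key descriptive variables. They are compared between arms with allowance for kebele clustering.

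Protocol section III.B describes the sized quantity in three ways:
- the "main outcome of interests (adoption of LAM and other modern method by 12-month PP", with p1 and p2 defined as proportions adopting LAM or another modern method;
- a sample large enough "to detect an increase of at least 10% contraceptive prevalence rate (CPR) in the intervention arm";
- p1 as "20% PP contraceptive uptake by the final round of observation in the intervention arm".

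The objectives (Protocol section I and the opening list of the SAP) speak of uptake through 12 months. Protocol Table 1 lists current use among the items asked of women. Protocol sections III.A and III.B follow women to 12 months postpartum, but Table 5 places the follow-up questionnaire at 6-9 months postpartum.

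**The concern.** Ever-use can only rise as the year goes on; the share of women currently using a method falls when women stop. The protocol's background argues from women's status: 47% of pregnancies after non-first births come at intervals under 24 months, "13% of women are pregnant before the end of the first year postpartum", and 19% of women 0-2 years postpartum use a modern method. Those figures depend on continued use as well as on starting.

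If continuation differs by arm, the primary result could show a clear gain while the gain in women using a method at one year is much smaller. No planned, adjusted estimate would say so. LAM sharpens the point without any assumed rate. The background limits breastfeeding protection to the first 6 months, and the protocol models LAM discontinuation only over that period. If LAM counts, a woman who used nothing else is a success at 12 months after that protection has ended.

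The three names for 20% vs 10% add to this, because a reader cannot tell which quantity the 80% power refers to.

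**Working it through.** **1. The plan's own figure.** Inputs from Protocol III.B: p1 = 0.20, p2 = 0.10, two-sided alpha 0.05 (z = 1.960), power 80% (z = 0.842), design effect 1.5. With mean proportion 0.15:

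n = [1.960 × √(2 × 0.15 × 0.85) + 0.842 × √(0.20 × 0.80 + 0.10 × 0.90)]² / 0.10² = (0.990 + 0.421)² / 0.01 = 198.96, or 199.

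199 × 1.5 = 298.5, rounded up to 299, as stated. Allowing for 20% loss, 299 / 0.80 = 373.75, so 374 against the stated 375. The arithmetic is the same whether 20% vs 10% means ever-use or prevalence; only the quantity to which the power refers changes.

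**2. If 20% vs 10% is ever-use: power for use at 12 months.** Let a share c of users in each arm still be using at 12 months, so the proportions are 0.20c and 0.10c. The documents give no value for c; 0.9 to 0.5 is an assumed range. Effective n per arm is 299 / 1.5 = 199.3, and

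power = Φ{[(p1 − p2)√199.3 − 1.960√(2p̄(1 − p̄))] / √(p1(1 − p1) + p2(1 − p2))}.

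For c = 0.8: [0.08 × 14.12 − 1.960 × √(2 × 0.12 × 0.88)] / √(0.16 × 0.84 + 0.08 × 0.92) = (1.129 − 0.901) / 0.456 = 0.50, and Φ(0.50) = 69%.

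| c (both arms) | Use at 12 months | Power at 299 per arm | n per arm for 80% power |
|---|---|---|---|
| 1.0 | 20% vs 10% | 80% | 299 |
| 0.9 | 18% vs 9% | 75% | 339 |
| 0.8 | 16% vs 8% | 69% | 387 |
| 0.7 | 14% vs 7% | 63% | 450 |
| 0.6 | 12% vs 6% | 55% | 534 |
| 0.5 | 10% vs 5% | 47% | 653 |

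The last column rounds n up before applying the design effect of 1.5.

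**3. If 20% vs 10% were prevalence instead.** Ever-use would then be higher. At c = 0.8 in both arms it is 0.20/0.8 = 25% vs 0.10/0.8 = 12.5%, and power for the SAP's primary outcome is 90%. If only the 10-point gap carried over, power would be 64% at 30% vs 20% and 55% at 40% vs 30%.

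**4. Unequal continuation (illustration only).** With ever-use fixed at 20% vs 10%, the primary result is 10 points throughout. Use at 12 months is:
- 80% continuing in both arms: 20 × 0.8 = 16% vs 10 × 0.8 = 8%, a gap of 8 points;
- 60% intervention, 80% comparison: 12% vs 8%, 4 points;
- 50% intervention, 80% comparison: 10% vs 8%, 2 points.

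The documents do not say which arm would stop more.

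**The case against.** The strongest reply is that the outcome answers the question asked. The objectives in both documents concern uptake, and ever-use by 12 months measures uptake. That stands, and it is why ever-use should remain primary.

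Two stronger readings are tempting and are not supported. A reader might infer that the trial was sized on prevalence and is analysed on something else. Prevalence appears as one label for rates that the same section defines as adoption and restates as uptake. The wording is inconsistent; the sizing is not shown to rest on prevalence.

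A reader might also infer that the plan could not reveal early stopping. SAP section A does compare stopping reasons and duration of use by arm, so heavier stopping in one arm could show there. What remains is narrower. Those summaries describe mainly women who started, and do not give the proportion of all interviewed women using a method at 12 months. They also have no covariate-adjusted model; the SAP offers propensity methods only if the arms differ substantially.

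The unequal-continuation figures are fairly called hypothetical. Implant refresher training for health extension workers in the intervention arm, and IUD and implant provision at health centers in both arms, leave the direction of any difference open. With equal continuation the ratio between arms is unchanged. The background statistics on birth intervals explain why status at 12 months matters; they are not themselves in error.

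**Conclusion.** The concern holds in a limited form. The primary outcome is valid for uptake, and 299 per arm is correctly computed. But starters who stop count as successes, the treatment of LAM is unstated, and a conclusion about women using a method at one year would have no planned, adjusted estimate behind it. The sample-size wording should be made consistent.

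How far uptake and use at 12 months diverge cannot be determined from the documents. Under equal continuation of 90% to 50%, power for use at 12 months is about 75% to 47%, taking the plan's design effect of 1.5 and 299 women observed per arm. A secondary role with a confidence interval is therefore appropriate. The gap is worth closing before results are seen and does not undermine the primary analysis.

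**What to change.** 1. Keep ever-use within 12 months as the primary outcome, and state whether LAM counts as a modern method.
2. Add a secondary binary outcome to SAP section A: using a modern method at 12 months postpartum. Women who have stopped or are currently pregnant are not using; women who switched to another modern method are using; state how LAM is classed. Analyse all interviewed women with the same adjusted, kebele-clustered logistic model, and report both outcomes with confidence intervals.
3. In Protocol III.B, replace contraceptive prevalence rate with uptake by 12 months, so that the sized quantity is the analysed one.
4. Reconcile the follow-up time in Protocol Table 5 (6-9 months postpartum) with sections III.A and III.B (12 months). Use at 12 months cannot be observed at 6-9 months, and ever-use within 12 months would be only partly observed.

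The cost is some wording and one more model. Current use is already among the items asked, so no new data are needed provided the interview takes place at 12 months. The drawback is a further secondary outcome, with the lower power shown above and possibly a less favourable result.

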The Ethiopian health system envisages that a number of health contacts should occur for women and babies from pregnancy through to the extended postpartum. Figure 1 below illustrates these contacts.

Figure 1: Possible Contacts with the Health System for Pregnant Women in Ethiopia

Month	4	5	6	7	8	9		1	2	3	4	5	6
Client	Pregnancy						Birth	Postpartum Period					
HDA	x	x	x	x	x	X	Home	X	x	x	x	x	x
HEW	Quarterly visits: 2-3 times during last two trimesters of pregnancy							Quarterly visits: 2-3 times during first 12 months postpartum					
HC	ANC1 Before end of 4 th month		ANC2 24-28 weeks	ANC3 32 weeks	ANC4 36 weeks	Facility		PNC w/in 48 hours; w/in 6 weeks					
								DPT1 6 weeks		DPT2 10-14 weeks		DPT3 14-22 weeks	

About 84% infants receive at least one dose and more than 60% receive two doses of basic vaccines. A substantial number of mothers also seek care for their child's fever, diarrhea and other illness from health providers. This study will take these contact occasions as opportunities for promoting PFP, but also to reinforce the need to fully vaccinate children.

III. Study Design

- A. Provide an overview of your study design and methods. The study design must relate to your stated aims/objectives. Details will be requested later. If your study also involves analysis of existing data, please complete Section XI, "Secondary Data Analysis of Existing Data" in the last part of this research plan. If your study ONLY involves analysis of existing data, please use the research plan template for secondary data analysis (JHSPH IRB Research Plan for Secondary Data Analysis of Existing Data/Specimens).

This implementation research will use a quasi-experimental mixed method design with two arms. The intervention arm will have integrated PFP messages at each level of health system contacts. The control arm will continue to deliver the existing FP services at primary health care centers only.

The primary study population is a cohort of pregnant women, enrolled between the 2nd and 3rd trimester of pregnancy in both arms, who will be followed to twelve months post-partum. We will interview the women at study enrollment and at the end of the study. We will track women's contacts with the health system, particularly regarding PFP counseling, decision making and contraceptive adoption, through chart reviews of routinely collected facility and community based health records and registers (e.g. family folders that may be modified for study).

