Health providers (at Health Center)	Mixed methods questionnaire (going through each point of service – ANC, delivery, PNC and immunization)	
 • Integration of PFPF messages in ANC • Delivery of contraceptive methods at birth, including PPIUD, or in postnatal contacts • Experience with scheduling mobile services or referrals for permanent methods • Barriers to PFPF counseling and service delivery, including stock outs, organization of services, manpower, confidence to deliver, etc. • Experience with record keeping and analysis of PFPF data
District (woreda) health managers	Key Informant Interviews	
 • Attitudes towards PFPF integration; • Barriers/Facilitators • Experience with data reviews, analysis of data to address gaps • Experience addressing management or systems issues with FP service delivery
Pregnant and postpartum Women	Census of all pregnant women in the catchment area Questionnaire for all women 6-9 months pregnant F/U and re-interview all women 1 year later Review Integrated MCH/Family Health Card	
 • Attitudes and use of FP – past use, current use (once delivered) • Family support for FP, spouse, MIL, FIL (ask who are most influential) • Attitudes on immunization, facility delivery, plans for delivery, infant feeding, care seeking for self or sick baby • # of health contacts, # of ANC visits, place of delivery, PNC visits at facility or home, immunization visits, BF practices, return to fertility, timing of adoption of FP if adopted, rationale for not, what was most influential for those who did adopt (and didn't)

Study Population	Data Collection Method	Type of Information/Data Collected
		
 Perception of risk of pregnancy and motivation to avoid another pregnancy Experience with woman held card, if brought with them to all contacts with the system; was it helpful? Ability to communicate method choice without card
Registers, Referrals at Health Center, Health post level	(Revised longitudinal register)	Ability to track pregnant women's PFP counselling, decision making on method choice and uptake of PFP # of women in register, completeness of register Follow up mechanism

The Table 2 provides details on the general study timeline, program activities and study related activities.

Timeline	Program Activities	Research-related Tasks
Preparatory phase (1 st 4-6 months)	Woreda level engagement of stakeholders	

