	Assessment of sampled health facilities readiness	Identification of data collectors
	Development and pretesting of SBCC and training materials for HEWs including how HEWs will train HDA (in adjoining woreda to avoid contamination)	Pre-testing of translated questionnaires for pregnant women and household members
	Development and pre-testing of HEW and HC M&E Tools	Abstraction tools for health records, development of monthly site monitoring visit documentation tool
	PPFP Counseling Training (2 day course, with more people)	Training of data collectors
	PPIUD/Implant Training (5 day course for subset)	
	Training of HEWs in PPFP counseling and promotion of PPFP messages at community level, assessment and refresher in implant skills	
Baseline		
 Census of pregnant women, enrollment of study participants (research team member paired with HDA team leader), Interviews of study participants and household members

Timeline	Program Activities	Research-related Tasks
Intervention implementation run time (15 months)	
 • HEWs train HDA team leaders and team leaders train HDA • Ongoing household visits by HDA and HEW and promotion of PFP at community level • Ongoing monthly meetings between HEWs and HDA team leaders – review of data on pregnant and recently delivered women • Post training follow up of PFP/trained health providers and HEWs 	Study Monitoring: 
 • Monthly F/U of HC records, tracking of births and PFP uptake among postpartum women using selected health facilities • Record review and abstraction of HEW data • Documentation of PFP, PNC or immunization service delivery issues
Endline (after 15 months)		
 • Follow up interviews with enrolled women • Interviews of HCW, HEW, • Focus Groups with HDA • In depth interviews of Woreda stakeholders
Analysis and report writing (4 months)		Data analysis Report Writing Journal Writing
Dissemination		Dissemination workshop in Ethiopia

B. Provide a sample size and a justification as to how you arrived at that number. If you use screening procedures to arrive at a final sample a table may be helpful.

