Study Population	Main Data Collection Method	Other Study Procedures	Number of contacts	Duration of Research Interview (Only)	Place of Interview
	Review Client held Integrated MCH/Family Health Card (post intervention)				
Registers, Referrals at Health Center, Health post level	(Revised longitudinal register) For HEW monitoring tool: Ease of use, helpful for data review meetings, etc		12: monthly data review and abstraction	N/A	Health Post and Health Center

4. Provide a brief data analysis plan and a description of variables to be derived.

After data have been thoroughly examined for quality, the study team will perform exploratory data analysis of the key variables for checking frequency distributions, measures of variability, central tendency, and data outliers. We will also check for incomplete data and undertake an imputation strategy, if needed.

We will examine the differences in contraceptive use behavior by study arms for the following outcomes:

- Baseline only: % with past use of postpartum family planning among women with non-first pregnancies
- % of postpartum women who choose a method prior to delivery (by # of ANC contacts)
- % uptake of FP by PP timing (Delivery, PNC, immunization) and type of method
- % of ANC and PNC contacts where FP was discussed or provided (by type of contact, i.e., HDA, HEW, HCW, other)
- Duration of exclusive breastfeeding/Introduction of complementary foods
- % initiated LAM and the duration of LAM use
- % of women received counseling during immunization
- Immunization coverage of infants of enrolled women by month postpartum (doses of DPT1, 2 and 3 and drop out rates)

We will perform both “intent to analysis” to examine the net differences between the two study arms, adjusted for confounding covariates, and “per-protocol analysis” to examine “dose-effect” of health system contacts. We will fit multivariable logistic regression models for examining the differences in binary outcome variables (e.g., method selection during ANC; FP discussions during contacts, etc). We will use hazards regression model for examining the duration (discontinuation) of LAM use in first 6-month PP and for analyzing the uptake of modern contraceptive method by timing since delivery.

1. Describe whether you are collecting or storing personal identifiers, and if yes, why you need them, and when and how you plan to dispose of them. Signatures on consent forms are considered to be identifiers.

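### The secondary outcome, method chosen before delivery, has no start of window, so a choice made before enrolment counts as a success in either arm

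*SAP*

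**What the plan says.** SAP section A names one secondary outcome: "Proportion of interviewed postpartum women who chose a method prior to delivery". The arms are to be compared by logistic regression, adjusted for clustering by kebele and for confounders that are not listed. The data analysis plan in Protocol section V.C carries the same outcome as the percentage "of postpartum women who choose a method prior to delivery (by # of ANC contacts"). Both texts close the period at delivery. Neither opens it at enrolment or at the start of the intervention.

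On entry, Protocol Table 1 has "Questionnaire for all women 6-9 months pregnant", and section III.B states "The eligible women in 3rd trimester who consent to participate in the study voluntarily will be recruited". The design overview in section III.A is looser, with women "enrolled between the 2nd and 3rd trimester of pregnancy in both arms". The exclusion criteria in section IV do not remove women who have already settled on a method.

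On sequence, Table 2 puts "Census of pregnant women, enrollment of study participants" in the baseline row. The implementation row that follows holds "HEWs train HDA team leaders and team leaders train HDA", together with household visits and community promotion by the volunteers (HDA) and the health extension workers (HEWs). Training of the HEWs themselves sits in the preparatory phase, before baseline.

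**The concern.** Figure 1 of the protocol schedules the first antenatal visit before the end of month 4, the second at 24-28 weeks, and monthly HDA contacts from month 4. Section III.A has gaps in health-centre services addressed in both arms before implementation. So there are occasions to choose a method before a woman enters the study, in either arm, and most of what separates the arms is listed after that point.

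Two things follow. Choices made before entry in equal shares add the same successes to both arms and hide part of any real effect. Unequal shares shift the estimate up or down. A null result could then mean that prenatal messaging did nothing, or that many choices were already made. A positive result could reflect a difference present at entry. The SAP does not say that choice at entry will be recorded, adjusted for, or used to restrict the analysis.

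**Working it through.** **Inputs from the documents** (Protocol section III.B): two-sided alpha 0.05, 80% power, 20% v 10%, design effect 1.5, 299 women per arm after follow-up. These figures belong to the primary outcome; no rate, effect or sample size is given for method choice.

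**Reproducing the plan's figure.** With p̄ = 0.15, the protocol's formula gives 198.96 per arm before clustering. Multiplied by 1.5 this is 298.4, rounded up to 299, as stated. Allowing for 20% loss, 299/0.8 = 373.75, or 374, against the stated target of 375. The effective size per arm is 299/1.5 = 199.3, and power at 20% v 10% is 80%.

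**Assumptions for the illustration** (not in the documents): a share s in both arms has chosen before entry and still counts as having chosen at delivery. Among the rest, 10% (control) and 20% (intervention) choose before delivery.

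**Equal shares.** Control proportion = s + (1 - s) × 0.10; intervention proportion = s + (1 - s) × 0.20; difference = (1 - s) × 0.10. Power = Φ{[d√n − 1.96√(2p̄(1 − p̄))] / √(p1(1 − p1) + p2(1 − p2))}, where d is the difference and n = 199.3 for all women. For women without a choice at entry, n = 199.3 × (1 - s) and the comparison stays at 20% v 10%.

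| s | All women, intervention v control | Difference | Power, all women | Power, no choice at entry |
|---|---|---|---|---|
| 0 | 20% v 10% | 10 points | 80% | 80% |
| 10% | 28% v 19% | 9 points | 56% | 76% |
| 20% | 36% v 28% | 8 points | 40% | 71% |
| 30% | 44% v 37% | 7 points | 30% | 65% |

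For s = 20%: 0.08 × √199.3 = 1.129; 1.96 × √(2 × 0.32 × 0.68) = 1.293; √(0.2304 + 0.2016) = 0.657; (1.129 − 1.293)/0.657 = −0.25, and Φ(−0.25) = 0.40.

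**Unequal shares.** Take 20% already chosen in one arm and 10% in the other.
- No true effect (10% choose in both arms), higher share in the intervention arm: 0.20 + 0.80 × 0.10 = 28% against 0.10 + 0.90 × 0.10 = 19%. This is a false difference of 9 points, with the same two proportions that a real effect gives at an equal s of 10%.
- True effect of 10% v 20%, higher share in the control arm: 0.10 + 0.90 × 0.20 = 28% against 0.20 + 0.80 × 0.10 = 28%. The effect disappears.

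The all-women proportions cannot tell these cases apart. Choice status at entry can.

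**The case against.** The strongest reply is that the share of all women with a method chosen by delivery is a legitimate coverage measure, and that equal shares of earlier choices dilute a difference without creating one. That stands, and it is why the all-women proportion should still be reported. It does not answer the unequal case.

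The size is also open to challenge. Neither s nor the effect on method choice is in the documents; the 10% v 20% is borrowed from 12-month uptake. The advantage of the restricted analysis is partly built in, because the illustration puts the whole effect in women without a choice at entry. It also assumes that choices do not lapse before delivery. All of this stands.

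Three stronger readings may tempt a reader, and the documents do not support them.

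- *That most women are past most antenatal contacts at entry.* With entry spread evenly over 26-40 weeks, (40 − 32)/14 = 57% would be past the scheduled 32-week visit. With 22-40 weeks it is 8/18 = 44%, and with 14-40 weeks 8/26 = 31%. The protocol's descriptions of entry differ, and these are scheduled visits, not attended ones. Section II reports that only 43% of women access any antenatal care.
- *That every choice before entry precedes the intervention.* HEWs are trained before baseline and no start date per kebele is given, so some earlier choices in the intervention arm could come from the programme.
- *That the dose-effect model is at fault for counting contacts before enrolment.* The SAP says "we will only include contacts during pregnancy since contacts after the birth would not have a temporal effect". That model runs regardless of arm, and Objective 1 of the protocol asks about existing contacts with the health system. Counting all pregnancy contacts is what was intended.

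Finally, the questionnaires are not among the documents. A baseline item may exist, and the protocol also plans record and card reviews that could help to date choices. The SAP ties none of these to this outcome.

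**Conclusion.** The point holds for the arm comparison of the secondary outcome. The definition has no start, entry is late in pregnancy in most of the protocol's descriptions, and the HDA cascade and household promotion are listed after baseline. Choices that precede most of the arm contrast therefore count. The dilution factor 1 - s is exact when shares are equal and choices persist. Bias from unequal shares is plausible with only two primary health care units per arm. The power figures (56%, 40% and 30% against 76%, 71% and 65%) show the direction and possible scale under assumed inputs; they do not estimate what this study will see. The primary outcome, use of a modern method within 12 months after birth, cannot be met at entry and is unaffected.

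**What to change.** 1. In the planned baseline interview, record whether the woman has already chosen a postpartum method, and which. If the item exists, say in the SAP that it will be used.
2. In the SAP, adjust the arm comparison of the secondary outcome for choice at entry. If every woman with a choice at entry is also counted as having chosen before delivery, that covariate predicts success perfectly; the logistic model then takes its arm effect from the other women, and the results should be shown by stratum.
3. Alongside the all-women proportion, report new choice between enrolment and delivery among women with no choice at entry.
4. Leave the dose-effect model on all pregnancy contacts. A count of contacts after enrolment is at most a sensitivity analysis.

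The cost is one or two questions, some SAP wording and a smaller denominator for the restricted analysis (299 × 0.8 = 239 per arm at an assumed s of 20%). The restricted analysis may also lose some real effect from HEWs trained before baseline, so it should accompany the all-women result and not replace it. SAP section C describes the extraction of service statistics in the past tense, so fieldwork may be well advanced. If baseline is complete without the item, report the outcome by gestation at entry and state the limitation.
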